7. STATISTICAL ANALYSES

Unless specified otherwise, longitudinal data will be presented by “before crossover” and “after crossover” periods, defined as:

- **“After crossover”** contain data collected after placebo subjects crossed over to AG-120. COS will be the analysis set.
- **“Before crossover”** contain AG120 arm data and the Placebo arm data up till crossover.

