Radiographic assessment (CT or MRI) for evaluation of disease response will be conducted every 6 weeks (± 5 days) for the first 8 assessments (ie, through week 48) and every 8 weeks (± 5 days) thereafter from C1D1, independent of dose delays and/or dose interruptions, and/or at any time when progression of disease is suspected. For subjects who discontinue study drug/placebo for reasons other than disease progression or start of another anticancer agent, an assessment will be conducted at the EOT Visit. Upon request by the Investigator, the subjects and site staff will be unblinded to treatment assignment after documented disease progression (as assessed by the Investigator) in consultation with the Sponsor Medical Monitor, and subjects randomized to the placebo arm who continue to meet eligibility criteria determined in the EOT visit will be given the opportunity to cross over to the active treatment arm and receive AG-120. For those subjects who cross over, placebo will not be counted as a prior line of therapy for the purpose of eligibility. If subjects cross over, they will start again with study procedures as at C1D1. These subjects will continue to be evaluated for tumor response by the Investigator. If the treatment assignment is determined to be AG-120 upon radiographic disease progression, the Investigator may consider continuing treatment with AG-120, provided the subject is clinically benefitting and there is no contraindication to continuing treatment beyond progression (see Section 9.8 for parameters for treating beyond progression). Target and non-target lesion selection and objective tumor response assessments per Response Evaluation Criteria in Solid Tumors (RECIST) v1.1 will be performed by the institutional radiologist(s). An independent central review of response will be conducted by an Independent Radiology Center (IRC) per RECIST v1.1. All scans will be sent to the IRC as detailed in the site-specific Imaging Core Manual (see Section 10.7.2).

HRQOL assessments will be conducted pre-dose on C1D1 and on Day 1 of every cycle thereafter until EOT. After EOT visit, the HRQOL will be conducted every 12 weeks until the start of new anticancer therapy. One additional HRQOL assessment will also be conducted at the safety follow-up visit. Health economic outcomes assessments will occur pre-dose on C1D1, C3D1, and at the EOT Visit. Compliance assessments will occur at C1D15, Day 1 of every cycle

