10.7.3. Health-Related Quality of Life Instruments

Subjects will complete the EORTC-QLQ-C30, EORTC-QLQ-BIL21, and PGI-S instruments prior to dosing on C1D1; subjects will complete the EORTC-QLQ-C30, EORTC-QLQ-BIL21, PGI-C, and PGI-S prior to dosing on Day 1 of every cycle thereafter until EOT. After EOT visit, HRQOL should be assessed every 12 weeks until the start of new anticancer therapy. One additional HRQOL assessment will also be conducted at the safety follow-up visit. If subjects cross over, they will follow the same assessment schedule as from C1D1. Completion of the questionnaires takes approximately 12 to 17 minutes. During the follow-up period (PFS and/or OS), sites should follow up with subjects to encourage them to complete the HRQOL questionnaires. During this time, the HRQOL instruments will be available online as a means to minimize missing entries and lost data. If a subject does not speak one of the provided languages for the EORTC-QLQ-C30, EORTC-QLQ-BIL21, PGI-C, or PGI-S, the subject will not be required to complete the instruments. (See Section 12.8.1 for the statistical aspects for managing such missing data.)

The EORTC-QLQ-C30 is a validated general questionnaire administered to assess HRQOL in subjects with cancer. The EORTC-QLQ-BIL21 was specifically designed to measure subject-reported issues related to symptoms, disease, and treatment in subjects with cholangiocarcinoma and gallbladder cancer. The PGI-C is a self-rated evaluative instrument for assessment of change from baseline across 3 domains and the PGI-S is a self-rated evaluative instrument for current severity of symptoms across the same 3 domains. For both the PGI-C and PGI-S, subjects will be asked to respond to 3 domain functions (physical function, appetite loss, and pain) for a total of 6 questions.

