8. EFFICACY ANALYSIS

For PFS, best overall response (BOR), ORR, DOR and other endpoints based on progression and/or response status, the primary analyses will be based on the independent central review by IRC. The endpoints based on Investigator assessment will be used as secondary analyses. Efficacy data after crossover will be analyzed separately.

After unblinding at local PD per Investigator assessment, subjects on AG-120 are allowed to stay on AG-120 if the treating Investigator deems they are clinically benefiting. The IRC will read all scans up to the discontinuation of AG-120. Subjects on placebo will no longer stay on placebo after radiographic disease progression and unblinding, hence no further scans will be read by IRC beyond the initial locally assessed disease progression imaging time point. Because of that, there is a potential systematic bias that subjects on the AG-120 arm could have PD called by IRC later than the locally assessed PD date; however, subjects on the placebo arm would systematically be censored by IRC analysis at the time of local PD if not concordant with local PD. To alleviate the potential imbalance between two arms, IRC assessments after the local PD from both arms will be excluded from the primary analysis of scan-related endpoints per IRC read. A sensitivity analysis by including all the scans read by IRC will be conducted.

All efficacy analyses will be based on the ITT set unless stated otherwise. If analyses are performed on more than one analysis set, the analyses on the ITT set will be considered primary. For each period, once the PD occurred, or the new anticancer therapy was initiated, all the subsequent tumor/response assessments will not be included in the tumor/response related summary analyses, but it will be included in the data listings.

Data after crossover (such as PFS) will be analyzed in a similar manner.

Listings for all efficacy endpoints will be provided.

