8.7.2. Statistical Analyses

8.7.2.1. QLQ-C30 and QLQ-BIL21 Analyses

Each scale will be transformed into a 0-100 score following EORTC guidelines:

- Estimate the average of the items that contribute to the scale; this is the *raw scale score*
- Use a linear transformation to standardize the *raw scale score*, so that it ranges from 0 to 100. $Scale\ score = (raw\ score - 1)/range * 100$. The only exception is Physical Function in QLQ-C30, where the scale score per EORTC QLQ-C30 manual is $[1 - (raw\ score - 1)/range] * 100$. Here, range is the difference between the possible

maximum and minimum response to each individual item. For instance, if the item is scored from 1 to 4, then $\text{range}=3$.

Transformed scores for each scale and the absolute change from baseline will be summarized by treatment and scheduled visit. A mixed-effect model with repeated measurements on the change from baseline across visits for key *scale scores* (such as pain, appetite loss, and physical function) over the course of before crossover period may be explored with baseline score, treatment, visit, treatment-by-visit as fixed effects, and subject as random effects.

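### The before-crossover quality-of-life comparison keeps AG-120 records after progression and possible unblinding but stops placebo crossovers at crossover, and no blinded-period analysis stands beside it

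*SAP*

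**What the plan says.** SAP Section 7 sets a default: "Unless specified otherwise, longitudinal data will be presented by “before crossover” and “after crossover” periods". The before-crossover data "contain AG120 arm data and the Placebo arm data up till crossover".

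The HRQOL sections follow that default. SAP 8.7.2.1 states: "Transformed scores for each scale and the absolute change from baseline will be summarized by treatment and scheduled visit". A repeated-measures mixed model "over the course of before crossover period may be explored". SAP 8.7.2.2 restricts the anchor-based work to the same period and, after unblinding, plots the cumulative distributions of change by arm. SAP 8.7.2.3 summarises EQ-5D-5L by treatment and visit and names no other period.

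On blinding, protocol 7.1 says that, on the investigator's request and with the Medical Monitor consulted, "the subjects and site staff will be unblinded to treatment assignment after documented disease progression". Protocol 7.1 and 9.8.1.2 and SAP Section 8 let AG-120 subjects judged to be benefiting stay on drug after progression. SAP Section 8 has placebo stop at progression and unblinding. Under protocol 10.7.3 the questionnaires are completed "prior to dosing on Day 1 of every cycle thereafter until EOT", then at safety follow-up and every 12 weeks until new anticancer therapy. Protocol Table 3 also marks them at the end-of-treatment (EOT) visit.

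For scans, SAP Section 8 recognises that the arms are observed differently after local progression: "To alleviate the potential imbalance between two arms, IRC assessments after the local PD from both arms will be excluded from the primary analysis". A sensitivity analysis with all IRC reads accompanies that rule.

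**The concern.** Comparing HRQOL with placebo is a stated secondary objective of a double-blind trial. After local progression the AG-120 side of a cycle-visit table can contain subjects who were kept on drug because they were doing well clinically and who may know that they take it. Almost no placebo subject can be in the matching position. The PGI-C is especially exposed, since it asks about change since study medication began.

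If the between-arm displays mix blinded and unblinded self-reports under different stopping rules, a reader cannot tell how much of a difference reflects the drug, how much reflects who was allowed to continue, and how much reflects knowledge of assignment. The SAP protects central reads of images from a related imbalance but does nothing comparable for self-reported data.

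**Working it through.** The documents give no HRQOL sample size, effect or power, so there is no planned figure to reproduce. The check is a trace of which records enter the comparison, followed by an illustration of size.

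**Step 1: records in the before-crossover period**

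| Record | AG-120 arm | Placebo, crosses over | Placebo, does not cross over |
|---|---|---|---|
| Cycle Day 1 before local progression | In, blinded | In, blinded | In, blinded |
| Cycle Day 1 after local progression, on assigned drug | In, possibly unblinded | About none; later AG-120 records go to the after-crossover period | About none |
| EOT visit | In, may follow unblinding | In, may follow unblinding | In, may follow unblinding |
| Safety follow-up and 12-weekly | In | Out once crossover starts | In, until new anticancer therapy |

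The second row carries most of the asymmetry. The last column shows why it is not complete.

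**Step 2: is there a cut elsewhere?** The both-arm cut in SAP Section 8 covers IRC reads for scan-related endpoints. The general exclusion after progression or new therapy in the same section covers tumour and response assessments. SAP 8.7 contains neither an HRQOL cut nor a sensitivity analysis.

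**Step 3: order of unblinding and EOT.** Unblinding follows documented progression. The EOT visit may fall up to 33 days after the last dose, and crossover eligibility is settled there (protocol Table 3, footnote 1). Nothing requires the questionnaires to come before the code is opened. EQ-5D-5L is collected only at C1D1, C3D1 and EOT (protocol 10.7.4), so one of its two scheduled post-baseline records is exposed.

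**Step 4: size, as an illustration.** From the documents: AG-120 median PFS of 6 months, exponential (SAP Section 5), so λ = ln 2 / 6 = 0.1155 per month. Assumed, because the documents do not give them: a share s of 20–50% of progressed AG-120 subjects continue, for an exponential time with mean m of 2–4 months (μ = 1/m). Deaths and other dropout are ignored.

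- On drug before progression at month t: A = exp(−λt).
- On drug after progression: B = s × λ/(μ − λ) × [exp(−λt) − exp(−μt)].
- Share of on-treatment records after progression: B/(A + B).

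Month 6, where A = 0.500:

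- s = 0.20, m = 2: B = 0.20 × 0.3005 × (0.500 − 0.0498) = 0.0271; share = 0.0271/0.5271 = 5.1%.
- s = 0.50, m = 4: B = 0.50 × 0.859 × (0.500 − 0.2231) = 0.1189; share = 0.1189/0.6189 = 19.2%.

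Month 9, where A = 0.354: the same formula gives 5.5% and 23.2%.

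The result moves with the assumptions. Suppose instead that a share c of progressed AG-120 subjects is still on drug at Day 1 of Cycle 7 (t = 28 × 6/30.4375 = 5.52 months). The proportion progressed is p = 1 − 2^(−5.52/6) = 0.47, and the share is cp/(cp + 1 − p): 18% for c = 0.25 and 47% for c = 1.

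These figures count records after progression. They are neither counts of unblinded records nor estimates of bias in a score.

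**The case against.** A reader might infer that the arrangement biases HRQOL in favour of AG-120. The documents do not support that. The extra AG-120 records come from subjects whose cancer has progressed, and decline after progression may lower the AG-120 mean. Selection of subjects who are doing well, and knowledge of active treatment, may raise it. The net direction is not determined.

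A reader might also infer that all post-progression records are open-label and that placebo contributes nothing. Neither follows. Protocol 9.6 makes unblinding at progression depend on an investigator's request, although SAP 8.8 states it without that condition, so progression and unblinding are not the same thing. Placebo subjects who do not cross over still give EOT, safety follow-up and 12-weekly records.

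The parallel with scans has limits too. The scan rule answers an event-ascertainment problem: the IRC reads no placebo scans past the local progression time point. HRQOL collection has no such stop. Cutting HRQOL at progression is a choice of estimand. With planned medians of 3 and 6 months it truncates placebo sooner, and it removes most progressors' EOT questionnaires. That argues against replacing the planned analysis, but not against reporting a truncated one beside it.

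Finally, the consequence is bounded. HRQOL lies outside the PFS–OS–ORR testing sequence, the plan is largely descriptive, and the mixed model is optional. All of this stands. What it leaves unanswered is that the stated comparison with placebo mixes blinded and possibly unblinded records under unequal stopping rules, with nothing planned to show the effect.

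**Conclusion.** The concern holds as an inexpensive improvement to a secondary, mainly descriptive comparison. The before-crossover period gives AG-120 records no end point and stops placebo crossovers at crossover, EOT questionnaires in either arm may follow unblinding, and no other rule in the SAP corrects this for HRQOL, PGI or EQ-5D-5L. The summaries, the mixed model if it is run, and the by-arm distribution plots are all affected.

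The extent is unknown because neither the continuation rate nor the unblinding rate is given. About 5–19% of on-treatment AG-120 records at month 6 would follow progression under the assumed 20–50% continuing for a mean of 2–4 months; other plausible inputs give more. The asymmetry is partial and the direction of bias is open. The primary PFS result and type I error control are untouched.

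**What to change.** 1. **SAP 8.7.** Add between-arm HRQOL, PGI and EQ-5D-5L summaries, and the mixed model if it is run, limited in both arms to records on or before the subject's unblinding date. Subjects never unblinded keep all their before-crossover records. Add a version cut at investigator-assessed progression. Report both beside the all-data before-crossover analysis, which stays, and flag every record as before or after unblinding.
2. **Protocol 9.6 and 10.7.3.** Where unblinding is requested because of progression, require the questionnaires due at that point (the EOT set for subjects who stop) to be completed before the code is opened, and record the order. Emergency unblinding is not touched.

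The cost is a few extra tables and one instruction to sites. The truncated versions will hold fewer records, including fewer placebo EOT and follow-up records. EQ-5D-5L loses most in relative terms because it has so few time points. For that reason the truncated results should supplement the planned analysis and not replace it.

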7.1. Subject Disposition

The disposition table of subjects will include the following categories:

- Number and percentage of subjects who are randomized (ITT set)
 - Number and percentage of subjects who are randomized but not dosed
 - Number and percentage of subjects who are randomized and dosed
- An end-of-treatment disposition (still on treatment vs. discontinued from treatment) based on SAS set. The primary reason for treatment discontinuation will also be included.
- An end-of-study disposition (still on study vs. discontinued from study) based on ITT set. The primary reason for study discontinuation will also be included.
- Placebo subjects who crossed over to AG-120 based on COS set. An end-of-treatment disposition (still on AG-120 vs. discontinued from AG-120) and the primary reason for discontinuing AG-120 will be summarized.

A listing of subjects who failed screening, including the reason for screen failures will be provided.

A listing of subjects including the date of first dose, date of last dose, date of crossover (if any), reason of treatment discontinuation, date of death, cause of death, end of study date, and the reason of study discontinuation will be provided.

7.2. Protocol Deviations

A subject-level protocol deviation listing will be provided by site and subject based on ITT set.

Major subject-level protocol deviations will be summarized, including:

- Number and percentage of subjects with at least 1 major protocol deviation.
- Subjects by number of major protocol deviations (1, 2, ≥ 3).
- Number and percentage of subjects within each major protocol deviation category.

7.3. Demographics and Baseline Characteristics

Baseline/demographics-related tables will be presented per randomization (ITT).

7.3.1. Demographics

Demographic and other baseline variables will be summarized for each treatment arm based on all randomized subjects (ITT set) and for the two treatment arms combined (total).

Subject demographic data, including age, gender, race, regions, and ethnicity (if available) will be obtained during screening.

Age (years), height (cm), weight (kg), body mass index (BMI) (weight [kg]/height [m²]), and other continuous baseline characteristics will be summarized descriptively (number of subjects, mean, standard deviation [SD], median, minimum, and maximum). Age category (<45, ≥45 - <65, and ≥65 years), sex, race, and ethnicity and other categorical variables will be summarized by frequency tabulations (count, percent).

If age is not collected in the database, it will be calculated as follows: age = [ICF year – birth year].

Body mass index will be calculated as follows: BMI (kg/m²) = weight in kg / (height in m)².

7.3.2. Baseline Characteristics

The following baseline characteristics will be summarized by treatment arms and for the two arms combined (total) based on ITT set. The variables will include:

- Number and percentage of subjects within each randomization strata (1 vs. 2 prior lines of therapy per randomization)
- IDH1 allele types per central IDH1 testing
- ECOG at baseline
- Cholangiocarcinoma type at diagnosis (Intrahepatic Cholangiocarcinoma, Extrahepatic Cholangiocarcinoma, Perihilar Cholangiocarcinoma, Unknown)
- T/N/M stage at initial diagnosis (Tx, Nx, Mx)
- Grade at initial diagnosis (Well differentiated, Moderately differentiated, Poorly differentiated, Undifferentiated, Unknown)
- Extent of disease at Screening
- Liver cirrhosis at Screening
- Presence of Biliary Stent at Screening
- Presence of Ascites at Screening
- Ascites related to Cholangiocarcinoma within the past 3 months
- Paracentesis with the past 3 months
- Pleural effusion related to Cholangiocarcinoma within the past 3 months
- Thoracentesis within the past 3 months

Baseline characteristic listing will be provided.

7.4. Prior Therapy and Medical History

7.4.1. Prior Systemic Anticancer Therapy

Prior therapies will be summarized for each treatment arm and for the two treatment arms combined (total) based on the ITT set. It will be summarized continuously as well as categorically. Types of therapies (adjuvant, palliative, etc.) will also be summarized.

This is the actual prior lines of systemic anticancer therapy subjects received in advanced setting in order to determine the study eligibility, not the stratification factor entered at the randomization. In majority of cases these two should match. However, it does not preclude the likelihood of mismatch due to mis-stratification, etc. A table will be provided to summarize the discrepancy between these two.

Duration of last line of therapy (in months) in advanced setting will be summarized, calculated as (end date of the last line of therapy – start date of the last line of therapy + 1)/(30.4375).

In case there are multiple drugs within 1 line of therapy, the outer window rule will be applied to calculate the duration: the earliest start date of all drugs will be the start date, and the latest end date will be the end date for that line.

The imputation of partial/missing dates is described in Section 10.6.

A data listing will be provided and the line that is contributed to the eligibility will be flagged.

7.4.2. Prior Local-Regional Therapy

A data listing will be provided for prior local-regional therapy, including the type of prior local-regional therapy, anatomical location, start date, end date, therapy setting, best response, and date of progression.

7.4.3. Prior Surgery for Cholangiocarcinoma

A data listing will be provided for prior surgery, including procedure, location, pathology finding, date of procedure, whether disease recur or progress after the procedure, and date of recurrence or progression.

7.4.4. Medical History

Medical history will be summarized by System Organ Class (SOC) and Preferred Term (PT), and sorted alphabetically in SOC and in PT. Medical history will be summarized by treatment arms and by both treatment arms combined (total) based on ITT set. A listing of medical history will also be provided.

7.5. Prior/Concomitant Medications and Procedures

A summary table of concomitant medications will be provided by treatment arms and total. Concomitant medications are those medications that were ongoing at the time of first dose or that were initiated after first dose but prior to last dose plus 28 days (inclusive). If an end date is missing or the medication is ongoing, the medication will be included as concomitant medications. Concomitant medications will be tabulated by anatomic therapeutic class (ATC;

level 4) and preferred term (PT). If the concomitant medication starts on or after the start of AG-120 upon crossover, it will be summarized in the “after crossover” table.

A summary table of concomitant procedures will be summarized by indication and preferred term. If the concomitant procedure starts on or after the start of AG-120 upon crossover, it will be summarized in the “after crossover” table.

In addition, the following data listings will be provided:

- A listing for prior and concomitant medications, with a flag to indicate prior vs. concomitant
- A listing of concomitant procedures

